### 2.3 Information regarding devices

All the data collected from the devices in this study listed above (i.e. mobile spirometry and actigraphy) are for research use only. This means that the data cannot be used for clinical patient management or as a primary clinical outcome measure.

## 3 RESEARCH METHODOLOGY

### 3.1 Study Design

This is a prospective study that will include two cohorts of patients (COPD and asthma) identified via EHR database analyses, study provider referral (COPD and asthma diagnoses with and without specialist confirmation), or recruited from sites of usual care. Participants will attend two visits with study team members at 0 and approximately 6 months, as most data will be captured either remotely via sensors and devices provided by GSK to the patients or via a data pull of EHR data. At the baseline visit, study team members will obtain written informed consent, distribute study devices, and provide instruction for proper use of study devices and platforms. Approximately six months later, at the second visit, the patient will return study devices. Patients will then be called to complete an exit interview to provide relevant feedback on the study.

### 3.2 Study Population

#### 3.2.1 Eligibility Criteria

##### 3.2.1.1 Inclusion Criteria

All patients will be selected based on the following criteria in EHR.

#### **Inclusion Criteria for COPD cohort:**

To be eligible to participate in this study, a subject must meet all of the following criteria:

- Provide signed and dated informed consent form.
- Be willing to comply with all study procedures and be available for the duration of the study.
- Age  $\geq$  40
- Diagnosed with COPD, defined as COPD listed on the patient's problem list and one of the following:
  - At least one inpatient hospitalization with a COPD diagnosis listed as the primary or secondary diagnosis (J41.x, J42.x, J44.x [chronic bronchitis], J43.9 [emphysema] or J44.9 [Chronic obstructive pulmonary disease, unspecified]) in the last 12 months OR
  - At least one emergency room encounter with a COPD diagnosis (J41.x, J42.x, J44.x, J43.9, J44.9) listed as the primary or secondary diagnosis in the last 12 months OR
  - At least two encounters of any combination of the following (each must be a distinctly different event with different dates of service):
    - an outpatient encounter with a diagnosis of COPD exacerbation (J44.1), Acute bronchitis (J20.x), or bronchitis (J40) listed as the primary or secondary diagnosis in the last 12 months, OR
    - an urgent care encounter with a COPD diagnosis (J41.x, J42.x, J44.x, J43.9, J44.9) listed as the primary or secondary diagnosis in the last 12 months
- At least one order for an inhaled COPD medication during the prior year

- 12+ months of data available in the integrated EHR data prior to date of screening

#### **Inclusion Criteria for Asthma cohort**

- Provide signed and dated informed consent form.
- Be willing to comply with all study procedures and be available for the duration of the study.
- Age  $\geq$  18
- Diagnosed with asthma, defined as asthma listed on the patient's problem list and one of the following:
  - At least one inpatient hospitalization with an asthma diagnosis (J45.x) listed as the primary or secondary diagnosis in the last 12 months OR
  - At least one emergency room encounter with an asthma diagnosis (J45.x) listed as the primary or secondary diagnosis in the last 12 months OR
  - at least two urgent care encounters, with different dates of service, with an asthma diagnosis (J45.x) listed as the primary or secondary diagnosis in the last 12 months OR
  - At least three or more prescriptions or prescription refills in the past 12 months for any combination of the following: an inhaled glucocorticoid with or without a second controller (Montelukast, Theophylline, a long-acting beta agonist [LABA] alone), or a combination drug with a LABA and an inhaled glucocorticoid
- 12+ months of data available in the integrated EHR data prior to date of screening

#### **Exclusion Criteria (screening question) for COPD cohort**

- Inability/Unwillingness to use the required devices, or
- Inability to read and understand English

#### **Exclusion Criteria (screening question) for Asthma cohort**

- Inability/Unwillingness to use the required devices
- Inability to read and understand English
- Diagnosis of COPD listed on problem list

### **3.2.2 Sampling**

PPD located in PPD has a service area that is largely rural, mostly Caucasian, remarkably stable population (i.e., a very low out-migration rate), and a higher percentage of elderly patients (aged 65+) than the national average.

PPD catchment area is one of the oldest and sickest in the nation in terms of multiple co-morbidities.

Patients will be selected based on the criteria previously described.

### **3.3 Study Visits**

#### **3.3.1 Recruitment**

The study team will utilize three recruitment methods. The first method is to have a Phenomic Analytics Clinical Data Core (PACDC) data broker identify potential participants through a data pull of EHR data or by review of PPD clinical dashboard. The second method is for study providers to refer eligible patients to the study team. The third method will have a study team member review the pulmonary clinics schedules and identify eligible patients. Potential subjects will be invited to participate.

#### **3.3.2 Baseline Visit**

A baseline clinic visit will be scheduled with interested patients and a study team member. At the visit, the potential participants will be informed of all pertinent details, risks, and benefits of the study via the study consent form. A study team member will answer any patient questions and patients will be given adequate time to consider participation. Written informed consent will be obtained using the study consent form. After consent, the participant will receive study devices and training on proper use of the devices. Patient vitals including height and weight will be collected by study staff. Participants will complete a baseline questionnaire. Data will be collected remotely from the devices and platforms for six months.

#### **3.3.3 Six Month Visit**

After six months (+/- 2 weeks), a second visit will be scheduled with the participant and a study team member. At the second visit, the participant will return the study devices and will complete an exit interview to obtain relevant feedback from the patient's perspective on the study. Exit interviews will be performed by PPD personnel.

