### **3.5 Data Source / Data Collection**

Integrated EHR records (primary and specialty care) are the key source for retrospective analysis and for identifying patients. Digital data collection from patient reports, devices, sensors, and EHR records over six months are the key sources for the prospective analysis. The full data integration will happen in two stages and a summary of variables to be extracted in each stage is included in Section 6.4. The study database will be housed on a third-party vendor's secure network. In the initial data integration stage and at the baseline visit, the study

team member will manually enter patient information (including name, MRN, date of birth, gender, ethnicity, date of consent, height, and weight) into the study portal built into the study tablet. The information entered into the study portal will calibrate the predictive formulas in the study devices and flow to the study database on the third-party vendor's secure network. Patients will then take the study devices home and use them as instructed. Data from the study devices, including the mobile spirometry device, the sensors for rescue and maintenance medications, activity monitors, and the ePRO platform will flow directly to the database on Vendor A's network. During stage one of the data integration, no EPIC data will be sent to the study database on the third-party vendor's secure network.

During stage two of the data integration, EHR data will be extracted and combined with device data in the database housed on Vendor A's network. Vendor A will de-identify the study database and send the data set to Vendor B. PPD staff will administer a study Exit Interview at the follow-up visit asking participants to provide feedback on the study, the study devices, and ePRO platform.

PPD data is part of the mini-sentinel monitoring system which means their data set meets standard criteria for data integrity and quality.

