### 3.6 Endpoints

We will be measuring the following:

- Spirometry
- Activity (Steps and daily activity)
- Patient experience of physical activity
- COPD symptoms Exacerbations (COPD cohort only)
- Rescue and maintenance medication use
- Primary care and secondary care visits specific to each cohort and in general,
- Number of days in hospital, new prescriptions, number of albuterol inhalers specific to each cohort
- CAT (COPD cohort) and ACT (asthma cohort)
- Exit Interviews

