### 6.3 Data Protection

All data collected in this study will be strictly confidential in accordance with all appropriate legislation. Data from study devices and ePROs will be encrypted and automatically transmitted to Vendor A. The portal that the study staff will enter patient information into during stage one of the data integration, including dates, participant names, MRNs, date of birth, gender, and ethnicity will be reviewed and approved by PPD. EHR data, including PHI such as names, dates, and MRNS, will be encrypted and sent to Vendor A via a PPD approved, secure portal. Vendor A's Insight Platform maintains a HITRUST certification to protect patient data. Vendor A will integrate the data from study devices, ePROs, and PPD on their secure network. Vendor A will de-identify the integrated study data set and transfer the de-identified data set to Vendor B.

Study staff will be instructed to maintain complete confidentiality of all collected data. Patient files will be kept on secure servers. The final study report will not contain any patient identifying information. Participants will be assigned a unique participant number in the final data set to ensure confidentiality and anonymity. Interview transcripts will be identified by this unique participant number and will not have any identifiers associated with the individual.

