### 6.4 Personally Identifiable Information (PII)

The final data set will be de-identified and will not contain PHI. However, Vendor A will have access to participant names, dates, date of birth, and MRNs to integrate data from multiple data sources including study device data, ePRO, EHR data, and Exit Interview transcripts. Vendor A will remove PHI elements from the dataset. PHI accessed for recruitment will only be seen by PPD staff. The final data set, housed by Vendor B, will be de-identified.

The data in the table below, including relevant dates, will be collected. The table also outlines who will have access to each type of data during each stage of data integration.

Stage One – Data Integration				
	PPD	GSK	Vendor A	Vendor B
Names	X		X	
Medical record number	X		X	
Telephone number	X			
Date of birth/date of death	X		X	
Height and weight	X	X	X	X
Information relevant to all encounters, admissions/discharges, clinical procedures, medications administered, problem list entries, and lab values	X			
Baseline demographic variables of patients (age, sex, ethnicity, tobacco use, comorbidities)	X		X	
Clinical outcomes and procedural related complications	X			
Information from study devices, sensors, and electronic platforms	X	X	X	X
Information gather from patient interviews at study visits	X	X	X	X

Stage Two – Data integration				
	PPD	GSK	Vendor A	Vendor B
Names	X		X	

Medical record number	X		X	
Telephone number	X			
Date of birth/date of death	X		X	
Height/ Weight	X	X	X	X
Information relevant to all encounters, admissions/discharges, clinical procedures, medications administered, problem list entries, and lab values	X	X	X	X
Baseline demographic variables of patients (age, sex, ethnicity, tobacco use, comorbidities)	X	X	X	X
Clinical outcomes and procedural related complications	X	X	X	X
Information from study devices, sensors, and electronic platforms	X	X	X	X
Information gather from patient interviews at study visits	X	X	X	X

Records of data generated in the course of the study shall be retained for at least 6 years and could be used for future research studies submitted and approved by the IRB.

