## Appendix 1. Schematic of a Prospective Study:

Clinic Visit 1  
Day 1

- Obtain informed consent
- Screen potential participants by inclusion and exclusion criteria
- Demonstrate devices
- Baseline data collection

During the 6-  
month study  
period

- Perform mobile spirometry weekly
- Wear the activity monitor daily
- Complete the diary card daily (for COPD subjects)
- Complete the CAT/ACT monthly
- Attach sensors to rescue and maintenance inhalers (where appropriate)

Clinic Visit 2  
Month 6

- Exit Interview
- Retrieval of devices

CONFIDENTIAL

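### No exit interview is provided for participants who leave early or miss Visit 2, so patient-experience feedback would come mainly from those who reach month 6

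*Combined protocol and SAP*

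**What the plan says.** Four places in the current protocol (Amendment 01) say when the exit interview happens.

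- Section 3.3.3, on the month-6 visit: "At the second visit, the participant will return the study devices and will complete an exit interview to obtain relevant feedback".
- Section 3.5, on what site staff will do: "administer a study Exit Interview at the follow-up visit asking participants to provide feedback on the study, the study devices, and ePRO platform".
- Appendix 1 lists "Exit Interview" under Clinic Visit 2, Month 6.
- Section 3.1 has devices returned at the second visit and continues: "Patients will then be called to complete an exit interview to provide relevant feedback on the study".

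Section 3.6 lists "Exit Interviews" among the endpoints, and Section 2.2 makes patient experience with the new collection methods a specific objective. Section 6.3 shows that the output is transcripts: "Interview transcripts will be identified by this unique participant number and will not have any identifiers associated with the individual". In Section 6.4 the matching row of both the Stage One and Stage Two tables reads "Information gather from patient interviews at study visits", which limits it to interviews held at visits. Section 3.7 plans for about 200 participants and at most 25% dropout. Section 4 leaves analysis detail to a full SAP.

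**The concern.** The exit interview is the only stated source of participants' views on the study, the devices and the ePRO platform. Every place that times it makes it depend on reaching Visit 2. The call in Section 3.1 shows that a telephone interview is already contemplated, but it comes after device return at that visit, so it is not a stated route for anyone who does not attend.

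This is a pilot whose rationale, in the synopsis, is to learn how to scale these methods to interventional trials. People who stop may know things about burden or usability that completers do not. Followed as written, the plan would describe mainly the experience of those who stayed. The limitations in Section 5 recognise selection at entry but not loss during follow-up. The bias could run either way, because illness as well as device burden can cause loss.

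**Working it through.** **1. Is there any route for early leavers?**

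| Section | Timing of the interview | Reaches someone who misses Visit 2? |
|---|---|---|
| 3.3.3 | At Visit 2 | Not as written |
| 3.5 | At the follow-up visit | Not as written |
| Appendix 1 | Under Clinic Visit 2 | Not as written |
| 3.1 | Call after device return at Visit 2 | Not as written |

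No section of the protocol text describes an early-termination visit, an interview at withdrawal, follow-up of a missed Visit 2, or collection of reasons for stopping.

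**2. Do other data fill the gap?** Section 3.5 says that "Data from the study devices, including the mobile spirometry device", together with sensor, activity and ePRO data, goes straight to the study database, so data sent before stopping are available. They show when use ceased, not why. Section 6.5 has tablet questions on device-related adverse events, which are not feedback on the study or its methods.

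**3. The plan's own figure.** Inputs: 200 participants, 100 per cohort (Sections 3.4.2 and 3.7); dropout of at most 25% (Section 3.7). Completers = 200 × (1 − 0.25) = 150, which matches the stated minimum of 150.

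**4. Participants who could go uninterviewed.** Only the 25% rate comes from the plan; 10% and 5% are assumed for range. Section 3.7 does not define dropout, so two variations are shown, both assumed: half of the dropouts still attend Visit 2, or all dropouts miss it and 10% of completers also miss or decline the interview.

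| Dropout | All dropouts missed | Half of dropouts still attend | All dropouts plus 10% of completers |
|---|---|---|---|
| 25% | 200 × 0.25 = 50 | 50 × 0.5 = 25 | 50 + 0.10 × 150 = 65 |
| 10% | 200 × 0.10 = 20 | 20 × 0.5 = 10 | 20 + 0.10 × 180 = 38 |
| 5% | 200 × 0.05 = 10 | 10 × 0.5 = 5 | 10 + 0.10 × 190 = 29 |

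The 50 would be 25 per cohort if loss is evenly split. These are illustrations, neither ceilings nor floors.

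**5. What an early-exit offer could recover** (acceptance of 25%, 50% and 75% assumed).

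- Of 50 leavers: 12.5, 25 and 37.5, or about 13, 25 and 38 interviews.
- Of 20 leavers: 5, 10 and 15 interviews.

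No percentage-point effect is calculated, because the output is transcripts and Section 4 defines no exit-interview proportion.

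**The case against.** The strongest reply is that this argues from silence. The consent form, the interview guide, the full SAP and Section 7 are not in the text available for review, and arrangements for early device return or recording a reason for stopping often sit in such documents. That stands as a limit: the finding is about what the protocol text provides, and it does not show that leavers will not be asked.

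Second, dropout in Section 3.7 is linked only to complete data. Someone who stops using the devices but comes to Visit 2 to hand them back would be interviewed there. This also stands, and is why 50 is not a ceiling and the half-attend column is shown. It does not help those who never return.

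Third, this is a feasibility pilot with no hypothesis tests, and the feedback is qualitative. That is a reason not to call the flaw fatal. It does not remove the problem, because patient experience is one of the things the pilot exists to learn.

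Fourth, reporting by completion status may rest on very few people: 10% dropout with 25% acceptance gives 5 interviews, or 2 to 3 per cohort. That is fair, and such results should be given as counts and themes. Reporting detail can go in the SAP, but the interviews must be provided for in the protocol, since no later analysis can supply them.

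**Conclusion.** The concern holds and should be fixed. On the protocol text, a listed endpoint serving a named objective would be collected mainly from participants who reach month 6. If dropout means not reaching Visit 2, about 50 of 200 could go unheard at the plan's 25% limit, and 20 or 10 at assumed rates of 10% or 5%. Under the alternative assumptions above, the count at 25% dropout runs from 25 to 65. The size and direction of any bias are unknown. No stated sample-size figure is wrong and the pilot is not invalidated. Separately, Section 3.1 (a call after the visit) disagrees with Sections 3.3.3, 3.5 and Appendix 1 (at the visit).

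**What to change.** In Sections 3.1, 3.3.3, 3.5 and Appendix 1:

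- Offer the exit interview at Visit 2, or at early withdrawal, early device return or a missed Visit 2. Allow it in person or by telephone, for every enrolled participant who has not withdrawn consent to contact.
- Record the mode, the date and the reason for stopping.
- Use one consistent description of when and how the interview is held.

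Amend the interview row in both Section 6.4 tables so that it is not limited to study visits, and the consent form if needed. In the report, give the number interviewed out of all enrolled, by cohort, and present experience findings by completion status; the detail can sit in the SAP.

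The cost is wording in four places, one row in each of two tables, and possibly a minor consent and IRB revision. The same staff would hold the extra interviews, using telephone numbers the site already has (Section 6.4): about 13 to 38 at 25% dropout, or 5 to 15 at 10%, with acceptance assumed at 25% to 75%. The documents give no interview length, so staff hours cannot be worked out. Some leavers will decline or be unreachable, so the gap will shrink rather than close, and those who accept will report on a shorter period of device use.

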### **3.4 Study Duration**

#### **3.4.1 Approximate Duration of Subject Participation**

Subjects will participate in the study for approximately 6 months.

#### **3.4.2 Approximate Duration of Study**

200 patients will be enrolled over an eight-month period, including 100 in the asthma cohort and 100 in the COPD cohort. Each patient will be followed for approximately six months after consent and enrollment into the study.

### **3.5 Data Source / Data Collection**

Integrated EHR records (primary and specialty care) are the key source for retrospective analysis and for identifying patients. Digital data collection from patient reports, devices, sensors, and EHR records over six months are the key sources for the prospective analysis. The full data integration will happen in two stages and a summary of variables to be extracted in each stage is included in Section 6.4. The study database will be housed on a third-party vendor's secure network. In the initial data integration stage and at the baseline visit, the study

team member will manually enter patient information (including name, MRN, date of birth, gender, ethnicity, date of consent, height, and weight) into the study portal built into the study tablet. The information entered into the study portal will calibrate the predictive formulas in the study devices and flow to the study database on the third-party vendor's secure network. Patients will then take the study devices home and use them as instructed. Data from the study devices, including the mobile spirometry device, the sensors for rescue and maintenance medications, activity monitors, and the ePRO platform will flow directly to the database on Vendor A's network. During stage one of the data integration, no EPIC data will be sent to the study database on the third-party vendor's secure network.

During stage two of the data integration, EHR data will be extracted and combined with device data in the database housed on Vendor A's network. Vendor A will de-identify the study database and send the data set to Vendor B. PPD staff will administer a study Exit Interview at the follow-up visit asking participants to provide feedback on the study, the study devices, and ePRO platform.

PPD data is part of the mini-sentinel monitoring system which means their data set meets standard criteria for data integrity and quality.

### 3.6 Endpoints

We will be measuring the following:

- Spirometry
- Activity (Steps and daily activity)
- Patient experience of physical activity
- COPD symptoms Exacerbations (COPD cohort only)
- Rescue and maintenance medication use
- Primary care and secondary care visits specific to each cohort and in general,
- Number of days in hospital, new prescriptions, number of albuterol inhalers specific to each cohort
- CAT (COPD cohort) and ACT (asthma cohort)
- Exit Interviews

